11.0 CENTRAL REVIEW PROCEDURES

11.1 Central Radiology Review

At the conclusion of the trial, a central review of x-rays and/or scans may be carried out if any responses have been claimed. For purposes of reporting, the results of both local and central radiology reviews will be included.

11.2 Central Pathology Review

There will be central pathology review for this study. Expert pathology review will be done for all patients to confirm the original diagnosis. At least one disease site specialty pathologist with recognized diagnostic expertise for the tumour type will review digital image from the original/recut HE slides and pathology report of the case. Another expert pathologist will be consulted to resolve significant diagnostic discordance if it arises. Results of the central pathology review will not be provided to the originating institution, the patient or patient record. The consistency of diagnosis of rare tumours will be assessed through central review of pathology specimens.

- 11.2.1 Patients with questionable local pathology (i.e. uncertain as to rare tumour diagnosis) *MUST have* their pathology reviewed by a Central Reference Pathologist to confirm eligibility BEFORE the patient can be registered on this study.
- 11.2.2 Archival primary tissue block or the following materials, will be required for central pathology review:
 - Original slides or one H&E stained re-cut on all tissue blocks (representative formalin-fixed if formalin is unavailable B5 block may be submitted).
 - Five unstained slides (pretreated for immunostaining) from each representative formalin-fixed tissue block. 5 additional unstained slides if B5 block is available and formalin is unavailable.
 - Copy of all pathology reports.
 - Copy of any ancillary reports, whether performed on the tissue, (i.e. immunophenotyping, cytogenics, molecular genetics, FISH etc.).

12.0 CORRELATIVE STUDIES

A detailed Correlative Studies Manual will be provided on the IND.228 trial specific website, which will include details regarding sample preparation, handling and shipping.

Specimens collected may be used by researchers to better understand the nature of rare cancers and how patients respond to treatment. Samples will be used for research purposes only and will not be sold. Patients will not be identified by name. The only identification of tissue will be by a patient study number assigned at the time of registration to the trial the surgical/ histology number and/or patient initials. Material issued to researchers will be anonymized and only identified by a coded number.

Testing for hereditary genetic defects predisposing to malignant disease will not be carried out without the expressed consent of the patient.

All patients on whom a diagnostic tumour block is collected will be aware of this retrieval and will have given their consent.

12.1 Protocol-Mandated Correlative Studies

12.1.1 Tissue Collection (Mandatory)

Archival Tumour Collection:

The submission of a representative block of the diagnostic tumour tissue at the request of the CCTG Central Tumour Bank is mandatory for participation in this trial. One tumour block and one adjacent normal tissue block are requested from any of the biopsies or resections of the tumour. If no primary cancer blocks are available, one block of metastatic tissue can be sent instead. The preferred tumour sample for the determination of a patient's PD-L1 status is the one taken following the completion of the most recent prior line of therapy.

Blocks are the preferred material to collect, as it is well known that tissue materials (including protein and nucleic acid integrity) on unstained sections deteriorate rapidly within 3-6 months after preparation. This will optimize the amount of tissue available to investigators and permit the preservation of the block submitted. If, at any time, the submitting hospital requires the block to be returned for medical or legal concerns, it will be returned by courier on request.

Where local centre regulations prohibit submission of blocks of tumour tissue, the approval of the CCTG must be sought prior to registering of the first patient to allow cores (two 2 mm cores of tumour from the block) and slides (see Section 11.0 for slide specifications) of representative tumour tissue to be substituted in response to the Central Tumour Bank request.

Diagnostic pathology reports are received as part of the supporting documentation required for this trial. Receipt of these will initiate a request directly from the Queen's Department of Pathology to pathology departments for a representative tumour block.

Planned Priority Assays on Tumour Tissue Include:

- PD-1, PD-L1.
- Evaluation of lymphocyte infiltration (TILs) including subtypes by immunohistochemistry (CD8 and FOXP3).
- Expression profiling of immune markers
- Genomic profiling.

12.2 PD-L1 and TILs Pre-Screening - Tumour Tissue Mandatory for Cohort 2 patients only.

Pre-screening for PD-L1 and TILs can occur at any time prior to registration. All patients must sign the pre-screening consent prior to tissue being sent. The screening tests will be performed on slides created from an archival tumour block.

The TILs infiltration will be assessed on H&E slides and PD-L1 and expression will be performed by quantitative immunohistochemistsry (IHC). Results will be made available within about 14 days.

Patients will not be identified by name. The only identification on the tissue will be a patient study number assigned at the time of registration to the trial, the surgical/histology number and/or patient initials. Material issued to researchers will be anonymized and only identified by a coded number.

Diagnostic pathology reports are received as part of the supporting documentation required for this trial. A copy should be submitted with the Baseline Folder

Testing for hereditary genetic defects predisposing to malignant disease will not be carried out.

Please refer to the IND.228 Laboratory Manual for details.

12.3 Blood Collection

The CCTG is interested in exploring the use of surrogate tissues such as serum and plasma in evaluating potential prognostic or predictive biomarkers, or as evidence of pharmacodynamics effects. Serum samples will be collected for planned studies from all patients.

Exploratory assays include:

• Genomic aberrations (mutations, copy number changes) from circulating cell-free DNA (cfDNA).

Detailed instructions for sample acquisition, preparation, and shipping are found in the IND.228 Laboratory Manual.

12.4 Genomic Analyses

Genomic analyses will be performed on tumour and normal DNA. Technologies for genome sequencing are rapidly evolving and the most appropriate methods will be considered at the time of execution. Methods available include: Copy Number Variation, Structural variation, Targeted sequencing of specific gene sets, Hybridization capture and high-throughput PCR, Exome sequencing, Whole genome sequencing.

12.5 Statistical Analysis

The relationships between the tumour response and genetic mutation statuses will be investigated using Fisher's exact test, while the relationships between the time to progression and genetic mutations will be investigated using the log-rank test. Statistical testing will not be conducted in this hypothesis generating evaluation.

13.0 STATISTICAL CONSIDERATIONS

13.1 Objectives and Design

This is a phase II study to investigate the efficacy of durvalumab and tremelimumab in 8 cohorts of patients with rare tumours. The study will accrue up to 160 patients in one treatment arm. Each disease cohort will be evaluated independently.

In order to minimize the expected number of patients treated in the event that the regimen proves to be very disappointing or very unsuccessful, a two-stage design will be used for patient accrual *[Simon 1989]*.

13.2 Primary Endpoints and Analysis

Primary endpoint of this study is objective response rate, defined as the proportion of response evaluable patients who had complete response (CR) or partial response (PR) as their best response as assessed by RECIST version 1.1 criteria (i.e. a 30% decrease in the sum of the longest diameters of the target lesions maintained for at least 4 weeks (CR), or complete disappearance of disease and cancer related symptoms, also maintained for at least 4 weeks (CR)). Early progression is defined as progressive disease at or prior to the first assessment. The exact 95% confidence interval for the response rate will be calculated. The median and range of the duration of response, defined as the time from date of CR or PR to the date when progression or death is observed, will be estimated based on Kaplan-Meier method.

Sample Size for Each of 8 Disease Cohorts

Stage 1 of Accrual: 10 response evaluable patients will be entered in the first stage. Using response hypotheses of $H_0 \le 5\%$ and $H_a \ge 25\%$, we would reject the drug at the end of the first stage of accrual if no responses were seen. Otherwise, additional 10 patients will be accrued to the cohort.

Stage 2 of Accrual: Additional 10 response evaluable patients will be accrued. We would accept the drug as active if four or more responses are observed from 20 patients accrued.

Significance Level and Power: The procedure described above tests the null hypothesis (H0) that the response rate is 5% versus alternating hypotheses (H1) that the response rate is 25%. The significance level (i.e. the probability of rejecting H0 when it is true) is α =0.02 and the power (i.e. the probability of rejecting H0, i.e. deciding the regimen is active, when H1 is true) is 0.76. In addition, if the true response rate of an agent is 10%, it would be identified as ineffective with probability of 0.87. If the true response rate of the agent is 30%, it would be identified as effective with probability of 0.88.

Since the eligibility will not initially be limited to patients with tumours expression of PD1/PDL1 and or TILs (with the exception of cohort 2); before closing the original cohort when no response was observed after the first stage of the accrual, where feasible, a minimum of 10 patients with tumours with TILs and/or PD-L1 expression will be included in the response analysis. This modified cohort may be expanded to the second stage of accrual if there is at least one response observed.

Accrual and Duration of Study

A minimum of 10 and maximum of 20 response evaluable patients per cohort will be accrued. Should a disease cohort meet or exceed its activity goal, and recruitment is not limiting, additional enrollment beyond 20 patients/cohort may be considered to improve the estimate of anti-tumour activity and exploration of biomarkers outcome correlations. Evidence of anti-tumour response in the first stage will lead to the implementation of *optional* fresh tumour biopsies in patients subsequently enrolled to allow for more detailed genomic analyses. If an unusually high level of activity is seen (i.e. > 4/10 patients with objective response) the data will be made available to AstraZeneca for regulatory submission.

Following a survey of the CCTG IND members, the minimum estimated recruitment is 10 patients/year/cohort. If after 2 years, fewer than 10 patients have been registered in any given disease cohort and no responses have been observed, that cohort will close to accrual due to lack of enrolment. The minimum number of patients recruited is estimated to be 70 and the maximum number is estimated to be 140, assuming some patients will be registered, while some cohorts will close early for inactivity or lack of accrual feasibility. The maximum number will be increased if there are cohorts which will be modified to include patients with TILs and/or PD-L1 expression or additional enrolment beyond 20 patients/cohort is considered.

Patients will be accrued from approximately 15 cancer treatment centres across Canada over a period of approximately 24-48 months.

Following accrual of 20 eligible patients on the OCCC cohort, it was decided to expand the sample size to include 20 additional patients since with a total of 40 evaluable patients, the half-length of the 95% confidence interval for the response rate would be reduced from 21% with 20 patients to 15% when the observed response rate is 35%. Exploratory analysis will assess for correlations between biomarkers and objective response.

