2.2. Rationale for the Combination of Durvalumab and Tremelimumab

Targeting both PD-1 and CTLA-4 pathways may have additive or synergistic anti-tumour activity because the mechanisms of action of CTLA-4 and PD-1 are non-redundant *[Pardoll 2012]*. The combination of nivolumab and ipilimumab to patients with advanced melanoma induced clinically and statistically significant improvement in PFS and response rate than those obtained with single-agent therapy in a randomized phase III trial *[Larkin 2015]*. The frequency of grade 3 and 4 immune related toxicity was higher but manageable. Treatment-related adverse events of grade 3 or 4 occurred in 16.3% of the patients in the nivolumab group, 55.0% of those in the nivolumab-plus-ipilimumab group, and 27.3% of those in the ipilimumab group. Importantly, responses appeared to be deep and durable *[Wolchok 2013]*. The higher response rate and improved survival suggests that the combination is able to induce an anti-tumour response in patients with cancers that are otherwise refractory to the individual agents.

Promising results have been observed in the recently published phase 1B study of combination durvalumab and tremelimumab in 102 patients with NSCLC [Antonia 2016].

We hypothesize that one or more rare tumours will be sensitive to the combination of durvalumab and tremelimumab and sensitivity will be linked to identifiable biomarkers.

The defined cohorts and rationale for testing the agents is provided in the following table:

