2.3 Rationale for Rare Cancer Cohorts

For this trial, recent scientific and clinical literature were reviewed to determine rare cancers that might rationally be expected to be sensitive to combined immune check point therapy. Currently, expression of immune markers, PD1/PDL1, immune cell infiltrate of tumour and high mutation load correlative with activity in at least some settings. In addition, early clinical trials and case reports support sensitivity of some rare cancers. The proposed tumour types, rationale and relevant references are provided in the table below. Furthermore, the trial is designed to enhance the operational efficiencies of the study by allowing the enrolment of multiple tumour histologies into separate cohorts. By including multiple rare tumour histologies, many more patients can be enrolled/site under a single protocol. The two agent combination activity can be assessed within a single common protocol and this will allow the generation of data on objective response.

	Rare Tumour Cohort	Comment/Rationale	References
1	Salivary carcinoma	Unmet medical need. SGTs are characterized by recurrent genetic alterations, particularly chromosome translocations.	[Rettig 2016; Matthew 2015]
2	Carcinoma of unknown primary with tumour infiltrating lymphocytes (TILs) and/or expressing PD-L1	Unmet medical need. A subset of CUPs have immune cell infiltration and may represent cancers sensitive to immunotherapies.	[Hampig 2016]
3	Mucosal Melanoma	Unmet medical need. Objective responses reported with nivolimab.	[Larkin 2015; Lian 2014]
4	Acral melanoma	Unmet medical need. Objective responses seen with ipilumumab	[Johnson 2015]
5	Osteosarcoma	High-grade osteosarcomas have complex chaotic karyotypes. Many immune signaling pathways are important in bone homeostasis. The success of the innate immune stimulant mifamurtide in the adjuvant treatment of non-metastatic osteosarcoma suggests that newer immune-based treatments are promising.	[D'Angelo 2014; Kansara 2014]
6	Undifferentiated pleomorphic sarcoma	Increased mutational load seen in these tumours may be predictive for response to immunotherapy agents	[Lim 2015]

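### Does offering the TIL/PD-L1 look only after 0/10 responses put a cohort with a worse start at an advantage in section 13.2?

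*Combined protocol and SAP*

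**What the plan says.** Section 13.2 sets a two-stage rule for each cohort. Ten response-evaluable patients enter first, and with no response the drug is rejected. "Otherwise, additional 10 patients will be accrued to the cohort", with no marker restriction. At the end, "We would accept the drug as active if four or more responses are observed from 20 patients accrued". The stated properties are a significance level of 0.02 at 5%, power 0.76 at 25%, probability 0.87 of being called ineffective at 10%, and probability 0.88 of being called effective at 30%.

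A further paragraph adds the marker step and its reason: "Since the eligibility will not initially be limited to patients with tumours expression of PD1/PDL1 and or TILs" (cohort 2 excepted). It applies "before closing the original cohort when no response was observed after the first stage of the accrual, where feasible, a minimum of 10 patients" whose tumours carry TILs and/or PD-L1 expression. Then: "This modified cohort may be expanded to the second stage of accrual if there is at least one response observed". No final cut is given for this modified cohort. Nor does the plan say whether marker-positive patients among the first ten count towards the minimum of ten.

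On going past 20 patients: "Should a disease cohort meet or exceed its activity goal, and recruitment is not limiting, additional enrollment beyond 20 patients/cohort may be considered". Sections 1.3, 12.1 and 13.4 cover the markers in all other cohorts: exploring their relation to response is an objective, PD-L1 and TILs are priority assays on mandatory tissue, and no formal testing is planned.

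**The concern.** The reason given for the step, that eligibility is not restricted by marker, applies just as well to a cohort with 1/10, or to one that ends at 1-3/20. Section 2.2 expects that "sensitivity will be linked to identifiable biomarkers", and section 2.3 cites "expression of immune markers, PD1/PDL1, immune cell infiltrate of tumour and high mutation load correlative with activity in at least some settings". If activity really is confined to marker-positive tumours, a cohort with 0/10 can be given an enriched second test. A cohort with 1/10 must reach four responses in an unselected population, and if it ends at 1-3/20 it has no marker-positive decision. At stake would be activity in a marker-defined subset, missed in cohorts that did slightly better at the start. Cohort 2 is already marker-selected and the clear cell ovarian cohort had 7/19 responses (section 2.3), so six cohorts could be affected.

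**Working it through.** **Base rule.** Inputs from section 13.2: 10 + 10 patients, stop at 0/10, active at 4/20 or more.

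P(active | p) = Σ over x = 1..10 of P(Bin(10,p) = x) · P(Bin(10,p) ≥ 4 − x)

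This gives 0.0153 at 5%, 0.1285 at 10% (1 − 0.1285 = 0.8715 called ineffective), 0.7622 at 25% and 0.8830 at 30%. All four stated figures are reproduced to two decimals.

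**The apparent reversal.** Assumptions not in the plan: the optional step is always used, the 4/20 cut is inherited, stage 1 marker-positive patients carry over, and marker prevalence π is 30%, 50% or 70%. Let p₊ and p₋ be the response rates in marker-positive and marker-negative tumours, and p = πp₊ + (1 − π)p₋.

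- After 1/10: P(Bin(10,p) ≥ 3).
- After 0/10, with k of the first ten marker-positive: P(x ≥ 1 and x + y ≥ 4), where x ~ Bin(10 − k, p₊) and y ~ Bin(10, p₊), averaged over k ~ Bin(10, π(1 − p₊)/(1 − p)).

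| p₊ / p₋ | After 0/10, π = 30 / 50 / 70% | After 1/10, π = 30 / 50 / 70% |
|---|---|---|
| 25% / 5% | 0.637 / 0.518 / 0.357 | 0.088 / 0.180 / 0.292 |
| 25% / 25% | 0.610 / 0.475 / 0.311 | 0.474 at each |
| 10% / 10% | 0.078 / 0.050 / 0.026 | 0.070 at each |
| 5% / 5% | 0.008 / 0.005 / 0.002 | 0.012 at each |

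The first row is the concern. The other rows show that it depends on the marker effect. At 5% in both groups, 1/10 does better at all three prevalences. At 10% in both groups it does better at 50% and 70%. At 25% in both groups the two are level at 50%, and 1/10 is ahead above that.

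**The result itself is evidence.** The table holds the true rates fixed, but 0/10 also makes an inactive drug more likely. Assume equal prior weight on an inactive drug (5%/5%) and a marker-driven one (25%/5%). At π = 70%, P(0/10) is 0.95¹⁰ = 0.599 for the inactive drug and 0.81¹⁰ = 0.122 for the marker-driven one. The weight on the marker-driven drug after 0/10 is therefore 0.122/(0.122 + 0.599) = 0.169, and the predictive chance is 0.169 × 0.357 + 0.831 × 0.002 = 0.062. After 1/10 the same calculation gives 0.145. At π = 50% the pair is 0.132 against 0.100; at 30% it is 0.224 against 0.054. So the ordering is lost at 70% even when a strong marker effect has half the prior weight.

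**What is being compared.** A positive result after 0/10 would concern marker-positive disease. After 1/10 it concerns the disease as enrolled. At π = 30% the overall rate is 0.3 × 25% + 0.7 × 5% = 11%, and section 13.2 intends a 10% agent to be called ineffective with probability 0.87. The low 0.088 is mostly that intended behaviour.

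**What the step does to the whole procedure.** At 25%/5%, the chance of a positive decision without it is 0.165 / 0.342 / 0.531. With it, add P(0/10) times the chance after 0/10:

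- π = 30%: 0.165 + 0.312 × 0.637 = 0.364
- π = 50%: 0.342 + 0.197 × 0.518 = 0.444
- π = 70%: 0.531 + 0.122 × 0.357 = 0.575

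The step only adds detection. It takes nothing from a cohort that continues.

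**Feasibility.** The contrast is largest at low prevalence, where the step is hardest to carry out. After 0/10 at π = 30%, the expected number of marker-positive patients among the first ten is 10 × 0.3 × 0.75/0.89 = 2.5. Reaching 20 means screening about (20 − 2.5)/0.3 ≈ 58 more patients. Section 13.2 estimates a minimum recruitment of 10 patients per cohort per year and accrual over 24-48 months, and the step is conditional on feasibility.

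**The case for a change.** The strongest reply is that the asymmetry is real under the protocol's own biomarker hypothesis. At 25%/5%, the chance of passing stage 1 and then ending below 4/20 is 0.523 / 0.461 / 0.347, the most likely outcome at 30% and 50% prevalence. Carry-over is also the reading less favourable to the concern. If all ten marker-positive patients must be new, the chance after 0/10 at 25% is 0.762, and with equal rates in both groups 0/10 stays ahead of 1/10 for any rate above about 3.3%. Giving the same look to cohorts that end at 1-3/20 with at least one marker-positive responder would raise the overall chance of a positive decision at 25%/5% to 0.738 / 0.771 / 0.777.

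The arithmetic stands, and so does the observation that the modified cohort's final cut and overlap rule are unstated. It does not show a fault. Even with new patients, the comparison conditions on a fixed true rate: with no marker effect and equal prior weight on 5% and 25%, the predictive chance is 0.079 after 0/10 against 0.184 after 1/10. The wider look is a trade-off. At 5%, the false-positive rate goes from 0.020 / 0.018 / 0.017 to 0.028 / 0.027 / 0.024. At 25%/5%, expected enrolment goes from 21.9 / 20.7 / 19.9 to 28.3 / 25.2 / 22.1 patients per cohort, in tumours chosen for their rarity. Removing the step instead would lower detection to the base figures. For a cohort at 1-3/20, the base rule already speaks only of the disease as enrolled, and the marker-response relation is already to be explored.

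**Conclusion.** The concern does not hold. The marker step operates at the point where a cohort would otherwise close for lack of any response. It is optional, depends on feasibility, and is not offered as a marker-positive decision for every cohort that falls short. A cohort with at least one response is not closing; it receives its second ten patients. Limiting extra enrolment to would-be closures is a defensible design choice in rare tumours.

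The reversal (0.637 / 0.518 / 0.357 against 0.088 / 0.180 / 0.292) is correct only under its assumptions: an inferred 4/20 cut, a fixed marker effect of 25% against 5%, a prevalence that the documents do not give, and a step that is always used. It also sets a claim about marker-positive disease beside one about unselected disease. The four operating characteristics in section 13.2 are tied to the two-stage procedure set out before the marker step, and they reproduce. The unstated cut and overlap rule are missing detail and make no stated rule or figure wrong.

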7	Clear cell carcinoma of the ovary(expanded to include 20 additional patients in Jan 2019)	Objective responses were noted in a phase 1b study of avelumab, anti-PD-L1 monoclonal antibody in clear cell ovarian carcinoma, and in a phase II clinical trial in heavily-treated platinum-resistant ovarian cancer, OCCC subtypes. In addition, promising emerging preclinical and clinical data supports the further development of immune checkpoint inhibitors in gynecologic cancers.	[Disis 2015; Oda 2018; Heong 2017]
8	Squamous cell carcinoma of the anal canal	Seven/33 evaluable patients (21%) had a partial response to nivolimab	[Morris 2016]

Rationale for the Expansion of the Clear Cell Ovarian Cohort:

The clear cell carcinoma of the ovary cohort (#7) met its accrual goal of 20 patients in April of 2018. Efficacy analysis showed objective responses in 7/19 patients, an overall response rate of > 30%. The combination was tolerable and toxicity profile was as expected for combined immune checkpoint inhibitors. Durvalumab/tremelimumab related events are mostly grade 1-2 with most common ones being fatigue, rash, diarrhea and hypothyroidism. Grade 3 related events reported as an SAE in this cohort were: auto-immune hepatitis in 2 pts, increased lipase (without pancreatitis), AA-amyloidosis, renal failure, colitis and rash. The majority of hematologic and biochemical events are grade 1-2, however anemia grade 3 was seen in 3 patients.

Given the activity seen and with new literature showing that OCCC both tumour cells and tumour microenvironment may be associated with sensitivity to immune checkpoint inhibitors *[Oda 2018]*, the cohort will be expanded an additional 20 more patients.

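### Does expanding the clear cell ovarian cohort after 7/19 responses, with no separate report of the expansion patients, make the pooled response rate misleading?

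*Combined protocol and SAP*

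**What the plan says.** Each cohort follows a two-stage design of 10 plus 10 patients (section 13.2). After the first stage, "we would reject the drug at the end of the first stage of accrual if no responses were seen". At the end of the second, "We would accept the drug as active if four or more responses are observed from 20 patients accrued". The interval method for the primary endpoint is also fixed there: "The exact 95% confidence interval for the response rate will be calculated".

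Section 13.2, under Accrual and Duration of Study, allows larger cohorts: "Should a disease cohort meet or exceed its activity goal, and recruitment is not limiting, additional enrollment beyond 20 patients/cohort may be considered". The stated aims are a better estimate of activity and work on biomarkers.

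For the clear cell ovarian cohort, section 2.3 reports: "Efficacy analysis showed objective responses in 7/19 patients, an overall response rate of > 30" percent. It continues: "Given the activity seen and with new literature showing" a link between tumour biology and sensitivity to checkpoint inhibitors, "the cohort will be expanded an additional 20 more patients". Section 13.2 then gives the statistical reason: "with a total of 40 evaluable patients, the half-length of the 95% confidence interval for the response rate would be reduced from 21" percent with 20 patients to 15% with 40, at an observed rate of 35%. The only analysis sentence that follows concerns biomarker correlations.

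Section 13 does not state how the two groups of patients are to be combined, and it plans no response rate for the expansion patients alone.

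**The concern.** A cohort is eligible for expansion only if its first 20 patients gave a good result, so among expanded cohorts the first 20 overstate the true rate on average. Adding 20 new patients dilutes the overstatement without removing it. The precision statement on 40 patients points to a single pooled rate with an ordinary exact interval, which takes no account of this selection.

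The new patients are the only ones whose results played no part in the decision to expand. If only the pool is shown, the planned analysis would not itself reveal whether they reproduced the earlier result. At stake would be an inflated response rate for the one cohort documented as expanded, and perhaps an interval that covers less often than 95%.

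**Working it through.** **Inputs.** From section 13.2: stop at 0/10; activity goal at least 4/20; expansion open to cohorts meeting that goal; 40 evaluable patients in all; exact 95% interval. From section 2.3: 7/19 observed and 20 patients added. The true response rate *p* is not in the documents. It is an assumption, taken from 10 to 40%.

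**The plan's own figures.**
- Half-length by the normal approximation, 1.96 × √(0.35 × 0.65 / n): 20.9 points for n = 20 and 14.8 for n = 40. These round to the stated 21% and 15%.
- Exact intervals are 15.4 to 59.2% for 7/20 and 20.6 to 51.7% for 14/40. The average half-widths are 21.9 and 15.5 points, less than one point wider in each case.
- Two-stage design: the probability of passing (not 0/10, and at least 4/20) is 0.0153 at 5%, 0.762 at 25% and 0.883 at 30%. At 10% the probability of being called ineffective is 0.872. The plan states 0.02, 0.76, 0.88 and 0.87. All agree after rounding.

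**Bias of the pool, given expansion.** Let X be the responses in the first 20 after the 0/10 rule. Suppose every cohort with X ≥ 4 is expanded. Then

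E(pooled rate) = [E(X | X ≥ 4) + 20p] / 40.

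At p = 25%, E(X | X ≥ 4) = 5.756.
- First 20 alone: 5.756 / 20 = 28.8%, a bias of +3.8 points.
- Pool: (5.756 + 5) / 40 = 26.9%, a bias of +1.9 points.

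Pooling halves the bias at every *p*, because the second 20 patients contribute none.

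| True rate | P(expand) | Bias of pool (points) | Coverage of exact 95% interval, n = 40 |
|---|---|---|---|
| 10% | 0.128 | +6.1 | 90.4% |
| 15% | 0.342 | +4.4 | 96.6% |
| 20% | 0.576 | +3.0 | 96.7% |
| 25% | 0.762 | +1.9 | 98.4% |
| 30% | 0.883 | +1.1 | 97.7% |
| 35% | 0.949 | +0.5 | 97.6% |
| 40% | 0.980 | +0.2 | 97.0% |

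Coverage drops below 95% only at the 10% row, where the goal is reached about one time in eight.

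Counting 19 first-phase patients, as in the reported 7/19, changes little: the bias is +3.3, +2.2, +1.3 and +0.7 points at true rates of 20, 25, 30 and 35%.

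**Pool against expansion patients alone.** At p = 25% the expansion patients alone have root mean squared error √(0.25 × 0.75 / 20) = 9.7 points. The pool has 6.4 points, bias included. At p = 35% the figures are 10.7 and 7.3.

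**All paths together.** Averaged over cohorts that stop, finish at 20 or expand, the simple observed rate is slightly low: −2.1 points at p = 25%. The upward bias is a feature of expanded cohorts only.

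**The case for a change.** The best argument for a change is that it costs almost nothing: a table row or two and a sentence. The expansion patients are the only ovarian data free of selection, and a drop among them could be hidden in the pool. If they gave 4/20 (20%), the pool would be 11/39 = 28.2% (exact interval 15.0 to 44.9%).

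The written rule also says only that expansion may be considered, so the trigger in practice could have been stricter than 4/20. If it was 7/20 (an assumption), the pooled bias is +6.9 points at a true rate of 25%. At 20% it is +8.8 points, and coverage falls to 84.5%.

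Part of this stands. The expansion was driven by response, the plan is silent on a separate rate, and listing the two groups beside the pool would be good reporting. The rest carries less weight:

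- No section states a trigger of 7/20. Using the observed count as the threshold is a choice made after the event. At a true rate of 20% such a trigger would be met with probability 0.087.
- A reader is not left blind. Section 2.3 prints 7/19 and gives it as a reason for expanding, so subtraction from the pooled count gives a fair approximation. It is only approximate, because one of the first 20 is uncounted and responses may be updated.
- A separate rate on 20 patients settles little. The exact interval for 4/20 runs from 5.7 to 43.7% and contains the earlier 36.8%.
- The precision sentence justifies a sample size. It does not confine the report to the pool.

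**Conclusion.** The concern is right in direction and too small to require a change. Under the written goal of at least 4/20, the pooled rate is high by about 0.5 to 3 points for true rates of 35% down to 20%. That is 3 to 20% of the planned 15-point half-length (0.5/15 and 3.0/15). Exact-interval coverage is 96.6 to 98.4% over true rates of 15 to 40%. The decision at 4/20 is made on the first 20 patients and is untouched.

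Pooling is a fair trade: it accepts a small bias for a clear gain in precision and serves the stated purpose of the expansion. Showing the two groups beside the pool is something an analyst can do without a rule in the plan, and it would alter neither the main estimate nor the conclusion. The 21% and 15% are sound planning figures for a decision already taken, so restating them by the exact method would gain nothing.

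This rests on two assumptions: that expansion followed the written goal, and that the true rate is not far below 15%. A much stricter unwritten trigger would make the bias larger, but the documents give no sign of one.
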